## Abbreviations

AE	Adverse event
Akt	serine/threonine protein kinase Akt
ALP	Alkaline phosphatase
ALT	Alanine aminotransferase
AMP	Adenosine monophosphate
AMPK	AMP kinase
AST	Aspartate transaminase
ATP	Adenosine triphosphate
BMI	Body mass index
Clin Lab	UAMS Clinical Laboratory
BSO	Bilateral salpingo-oophorectomy
BUN	Blood urea nitrogen
CCTO	Cancer Clinical Trials Office
CO 2	Carbon dioxide
ECC-1	Endometrial carcinoma cell-1
ELISA	Enzyme-linked immunosorbent assay
ER	Estrogen receptor
Erk1/2	Extracellular signal-regulated kinases 1 and 2
FASN	Fatty acid synthase
HbA 1c	Hemoglobin A 1c
HDL-C	High-density lipoprotein cholesterol
HEC-1B	Human endometrial carcinoma-1B
hTERT	Human telomerase
IGF-I	Insulin-like growth factor -1
IGF-II	Insulin-like growth factor -2
IHC	Immunohistochemistry
IRB	Institutional Review Board
IUD	Intrauterine device
Ki67	Antigen KI-67
KRAS	v-Ki-ras2 Kirsten rat sarcoma viral oncogene homolog
KLF9	Kruppel-like factor 9
LDL-C	Low-density lipoprotein cholesterol
mg	Milligram
miR	Micro RNA
mRNA	Messenger RNA
NIH/NCI	National Institutes of Health/National Cancer Institute
NTU	Non-tumor uterine
PCOS	Polycystic Ovarian Syndrome
PI	Principal Investigator
PR	Progesterone receptor
PTEN	Phosphatase and tensin homolog
RT-PCR	Reverse transcriptase polymerase chain reaction
SD	Standard deviation

TUNEL Terminal deoxynucleotidyl transferase dUTP nick end labeling  
UTR Untranslated region  
UAMS University of Arkansas for Medical Sciences

## Study Schema

## Study Summary

Title	A Randomized Pilot Study to Evaluate the Effects of a Short Course of Metformin versus No Therapy in the Period Prior to Hysterectomy for Grade 1-2 Adenocarcinoma of the Endometrium in Obese Non-Diabetic Women
Short Title	Effect of Metformin on Proliferation Markers in Endometrial Cancer
Protocol Number	138647
Phase	Pilot study
Methodology	A randomized open-label study of metformin vs. no metformin
Study Duration	18 months
Study Center(s)	Single-center
Objectives	To determine metformin tolerability. To determine metformin effect on tissue markers of proliferation, apoptosis, and insulin-mediated signaling. To determine metformin effect on a number of different markers measured in blood and plasma. To determine metformin effect on mRNA levels and miR profiles.
Number of Subjects	40 total: 20 metformin, 20 control
Diagnosis and Main Inclusion Criteria	Obese (BMI≥30) non-diabetic women with newly diagnosed Grade 1-2 adenocarcinoma of the endometrium
Study Product(s), Dose, Route, Regimen	Metformin 500 mg po bid x 14 - 21 days
Duration of administration	14-21 days
Reference therapy	Non-treatment arm
Statistical Methodology	Wilcoxon rank-sum tests will be used to compare treatment arms for differences in each study endpoint.

## Protocol Summary

This is a randomized, open-label clinical investigation of the effects of short-term oral metformin therapy on biomarkers for tumor growth in subjects with endometrial cancer. Metformin is a well-tolerated drug widely prescribed for treatment of Type 2 diabetes mellitus and for treatment of Polycystic Ovarian Syndrome (PCOS) in non-diabetic women. Clinical trials are ongoing to explore this possibility in breast cancer (NCT01101438). This investigation is the first study of metformin in endometrial cancer patients, and is designed to understand the mechanism of its anti-cancer actions, if any, and its interactions with biomarkers in endometrial cancer patients.

Forty non-diabetic subjects will be randomized so that 20 will receive oral metformin for 14-21 days and the remaining 20 will receive no metformin for 14-21 days. Subjects will be monitored for adverse events (AEs). All subjects will have blood samples collected on Day 1 (prior to start of metformin for subjects randomized to metformin) and prior to surgery. These samples will undergo metabolic, lipid and tumor-specific biomarker analyses. Tumor and adjacent normal tissue taken from subjects from the diagnosis and at the time of surgery will be analyzed for cellular proliferation, apoptosis and biomarker levels.

The **Primary objectives** of this study are as follows:

1. To determine the effect of metformin on tissue markers of proliferation, apoptosis, and insulin-mediated signaling in endometrial cancer in non-diabetic obese women.
2. To determine the tolerability of a short course of metformin in non-diabetic obese women with newly diagnosed endometrial cancer.

The **Secondary objectives** of this study are as follows:

1. To determine the effect of metformin on HbA1c and blood lipid profiles measured at baseline and just before surgery.
2. To determine the effect of metformin on the following hormones measured in blood plasma at baseline and just before surgery: Insulin, IGF-I, leptin, and adiponectin.
3. To determine the effect of metformin on the expression levels of mRNAs and miRs measured in blood plasma at baseline and just before surgery.
4. To determine the effect of metformin on the expression levels of mRNAs and miRs measured in tumor and adjacent non-tumoral uterine tissue.

## Background and Rationale

Endometrial cancer is the most common gynecologic malignancy in the United States, with approximately 45,000 cases per year. The single biggest risk factor for development of this disease is obesity. There is a direct correlation between the extent of obesity and the development of endometrial cancer. Peripheral adipose tissue contains high amount of the enzyme aromatase, which converts androstenedione into estrone. This source of estrogen then exerts a proliferative effect on the lining of the uterus, leading over time to endometrial hyperplasia and carcinoma. This type of endometrial cancer is referred to as Type I and represents ~80% of all endometrial cancers in this country. More recently it has been shown that obesity is a risk factor for insulin resistance leading to higher levels of circulating insulin. If the insulin resistance is great enough, obesity will lead to diabetes.

Serum insulin levels have now been shown to have a direct correlation with the development of endometrial cancer. Case-control studies have documented higher serum

insulin levels in women who develop endometrial cancer versus women who underwent gynecologic surgery for benign disease. Both insulin and insulin-like growth factor 1 (IGF-1) are highly associated with endometrial cancer. In one study, women with high circulating insulin levels had a hazard ratio of 2.33 for developing endometrial cancer versus women with low levels of insulin, after adjusting for age and estradiol.

High insulin levels are associated with the metabolic syndrome, which includes insulin resistance, elevated circulating hormones, obesity, elevated lipids, and can clinically manifest as anovulation and infertility. The metabolic syndrome in women is often referred to as the polycystic ovarian syndrome (PCOS). In these women, medical reduction of circulating insulin leads to improvements in all factors associated with the metabolic syndrome, including an increase in ovulatory cycles and improved pregnancy rates. Metformin, a biguanide compound, is a primary therapy used to treat insulin resistance associated with type II diabetes. Among diabetics on metformin, there is a reduction in the development of cancer and the rate of cancer death. It is not precisely known how metformin reduces the development of cancer. The reduction in cancer is not seen with other diabetic treatments such as sulfonylureas and insulin.

Since the early 1990s, metformin has been used to treat PCOS. A meta-analysis of the use of metformin and polycystic ovary syndrome in 2003 documented from controlled trials a significant improvement, compared with placebo, in ovulation rates, pregnancy rates, fasting insulin levels, blood pressure, and cholesterol. It is important to note that these studies were performed in non-diabetic women. Metformin is now used routinely as therapy for PCOS.

Because high circulating levels of insulin have been associated with the development of endometrial cancer, reduction of insulin levels with metformin may have a direct effect on the development or maintenance of this cancer. Anecdotal reports have occurred of women with early low-grade endometrial cancer being successfully treated with a regimen including metformin. Also, women who had initially responded to progesterone therapy for endometrial cancer and then became resistant, showed a renewal of progesterone response when they were started on metformin. Laboratory data has documented that metformin is a potent inhibitor of endometrial cancer-cell proliferation. Metformin has also been shown to promote progesterone receptor expression in endometrial cancer cells and to reverse progesterone resistance in endometrial cancer cells by several different mechanisms. Progesterone receptor expression and sensitivity in endometrial cancer are associated with improved clinical outcomes.

Arkansas is one of the top states for obesity in the United States. More than 30% of the adult population is characterized as obese, with a Body Mass Index (BMI) of 30 or higher. At UAMS, we see approximately 160 new cases of endometrial cancer in obese women each year. Most of these women are not diabetic, but are at risk for developing diabetes.

The present study proposes to treat obese endometrial-cancer patients with a four-week course of metformin prior to their definitive surgical therapy. This information will be used to apply for further funding to determine the exact role metformin may have in treatment of endometrial cancer. This drug also has the potential to be a chemo-preventive agent in women at high risk for developing endometrial cancer. There is currently no randomized trial to investigate the influence of metformin on endometrial cancer in obese non-diabetic women.

## Proliferation Markers

Human endometrial cancer cell lines ECC-1 and Ishikawa, when treated with metformin, showed decreased proliferation and decreased hTERT expression relative to non-treated cells. In women treated with metformin to manage PCOS, sera from PCOS women after 6 months of metformin significantly decreased the invasive properties of ECC-1, in part, by attenuating pro-inflammatory NF- $\kappa$ B expression and activation of Akt and Erk1/2 pathways. Further, the increase in progesterone receptor expression in metformin-treated Ishikawa and HEC-1B cells was associated with pathways targeted by adipokines and insulin.

In this pilot study, we will evaluate the effect of metformin on endometrial tumor-cell proliferation and apoptosis, obesogenic and pro-tumorigenic marker gene expression, and anti-oncogenic micro-RNA (miR) expression. miRs are potentially important regulators of expression of tumor-enhancing and tumor-suppressing pathway components. Endometrial tumors and adjacent non-involved tissues will be obtained at surgery. Tissues will be processed for histopathology and immunohistochemistry, and frozen in liquid nitrogen for RNA and protein analyses. Fasting blood sera will be obtained prior to and after the 14-to-21-day treatment period for measurement of insulin, adiponectin, leptin, and IGF-1 levels. Fixed tumor and 'normal' tissues will be analyzed for markers of proliferation (Ki67; phospho-histone H3) and apoptosis (TUNEL), and for expression of estrogen receptor (ER) $\alpha$ , progesterone receptor (PR), and tumor suppressor PTEN by immunohistochemistry. Isolated tissue RNAs will be assessed for PR, PTEN, ER $\alpha$ , KRAS, and hTERT transcripts by quantitative RT-PCR. Protein extracts will be evaluated by Western immunoblotting for PR, PTEN, total and activated Akt and Erk 1/2, and insulin receptor expression. Sera from both groups at both time points will also be subjected to analysis using miR-profiling arrays. Data obtained from analyses of all biological endpoints will be compared using standard statistical procedures.

The efficacy of metformin in potentially reversing the pro-tumorigenic parameters of endometrial cells (to be evaluated in adjacent non-involved endometrium) has not been previously explored. Our studies may provide information on a subset of patients who are more likely to respond to metformin based on their endocrine profiles and clinico-pathologic factors, and hence may lead to metformin as a standard chemopreventive strategy for women with high risk for EC. The analyses of metformin-responsive miRs that are associated with EC may also offer non-invasive biomarkers for predicting women diagnosed with lower stage of EC and who are likely to suffer from EC recurrence.

## **Trial Objectives**

### **Primary Objectives**

1. To determine the effect of metformin on tissue markers of proliferation, apoptosis, and insulin-mediated signaling in endometrial cancer in non-diabetic obese women. Specifically, to determine the effect of metformin on the following tissue markers measured in tumor and adjacent non-tumor uterine (NTU) tissue:
  - a. Proliferation: Ki67, phosphorylated histone H3, estrogen receptor (ER), progesterone receptor (PR), and telomerase (hTERT).

- b. Anti-proliferation and apoptosis: PTEN, KLF9, cleaved caspase-3, and TUNEL staining.
  - c. Insulin-mediated signaling: total and phosphorylated versions of Akt, Erk1/2, AMPK, and receptors for Insulin, IGF-I, and IGF-II.
2. To determine the tolerability of a short course of metformin in non-diabetic obese women with newly diagnosed endometrial cancer.

### **Secondary Objectives**

1. To determine the effect of metformin on HbA1c and blood lipid profiles measured at baseline and just before surgery.
2. To determine the effect of metformin on the following hormones measured in blood plasma at baseline and just before surgery: Insulin, IGF-I, IGF-II, leptin, and adiponectin.
3. To determine the effect of metformin on the expression levels of mRNAs and miRs measured in blood plasma at baseline and just before surgery.
4. To determine the effect of metformin on the expression levels of mRNAs and miRs measured in tumor and adjacent NTU tissue:

### **Exploratory Objectives**

1. To examine how BMI influences tumor-cell responses to treatment with metformin.
2. To explore the possible interactions of BMI, the plasma miR profiles and tumor and tumor mRNA profiles in final responses of endometrial tissue to metformin.

### **Trial Design**

This is a single-center, two-arm, open-label, randomized proof-of-concept pilot study to ascertain the therapeutic potential of metformin in obese women with Type I endometrial cancer. Forty non-diabetic obese subjects with confirmed stage I or II adenocarcinoma of the endometrium will be recruited from the University of Arkansas for Medical Sciences (UAMS).

#### **A. Method of assigning subjects to treatment groups.**

Subjects will be assigned randomly to one of two groups. Group 1 will receive treatment with metformin, while Group 2 will receive no treatment. Subjects assigned to Group 1 will be administered oral metformin at 500 mg twice a day for 14-21 days followed by surgery. These doses are therapeutic, and will permit patients to undergo their surgical therapy within an appropriate time frame.

Subject eligibility will be established before treatment randomization. Once a subject's eligibility is determined, the Research Staff will be notified to implement the randomization process. Randomization will be completed when the Research Staff receives a copy of the signed consent and the physician's orders for study agent to be dispensed.

To minimize imbalance between treatment arms, the randomization procedure will employ a stratified block randomization with randomly chosen blocks of size 2, 4, and 6, and with BMI as the stratification factor. Randomization will be conducted using sealed envelopes located at the Cancer Clinical Trials Office (CCTO). There will be two sets of consecutively numbered envelopes, one set for subjects with BMI from 30 to 39.9 and one set for subject with BMI of 40 or higher. At each randomization, the lowest numbered envelope will be chosen. The Research Staff will open the envelope and assign the subject to the treatment arm based on the contents of the envelope. The appropriate treatment will then be dispensed to the subject.

Methods for ensuring blinding.

Not applicable: this is an open-label study.

Methods for unblinding the study.

Not applicable: this is an open-label study.

Procedure for unblinding in case of medical emergency.

Not applicable: this is an open-label study.

Metformin will be administered to patients (randomized to receive metformin) for a minimum of 14 days and a maximum of 21 days, representing the typical time interval between confirmation of tumor diagnosis and surgical resection. Following surgical resection, any unused study drug will be returned to the physician at the time of the subject's first post-operative visit.

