## Statistical Considerations

General approach: For each tissue endpoint, the tumor-NTU difference will be calculated in each patient as the paired difference in values between tumor and adjacent NTU tissue. For each blood endpoint, the endpoint response to treatment will be calculated in each patient as the paired difference between post-study and pre-study values. All data will be summarized by treatment arm as the mean, standard deviation (SD), median, and range, and will be graphed as box plots. Tumor-NTU differences and endpoint responses will be compared against zero via signed-rank test within each treatment arm. Treatment arms will be compared to each other for differences via Wilcoxon rank-sum tests, with additional details provided below. All statistical comparisons will be two-sided, and will employ a 10% alpha to reduce Type II error in this pilot proof-of-concept study.

Analysis plan for tolerability: Meformin-related adverse events will be summarized by type and treatment arm, both as proportions at each grade and as average grades (i.e., mean scores). For each type, the Wilcoxon rank-sum test will be used to compare treatment arms for differences in average grade.

Analysis plan for the IHC-based primary endpoints: The IHC-based primary endpoints will be measured in tissue, and will include markers of proliferation (Ki67, phospho-histone H3, ER $\alpha$ , PR, and hTERT), anti-proliferation and apoptosis (PTEN, KLF9, cleaved caspase-3 and TUNEL staining), and insulin-mediated signalling (total and phosphorylated versions of Akt, Erk1/2, AMPK, and receptors for Insulin, IGF-I, and IGF-

II). Endpoints measured in tumor tissue, adjacent NTU tissue, and tumor-NTU differences will be summarized and graphed as described above. Wilcoxon rank-sum tests will be used to compare endpoints measured in tumor, and likewise endpoints measured in adjacent NTU tissue, for differences between the metformin and no-metformin treatment arms.

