Analysis plan for secondary endpoints measured in blood or plasma: The secondary endpoints measured in blood will be the levels of HbA1c, cholesterol, HDL-C, LDL-C, and triglycerides. The secondary endpoints measured in plasma will be the plasma hormone levels (Insulin, IGF-I, IGF-II, leptin, and adiponectin) and the plasma-measured expression levels of mRNAs and miRs. Endpoints measured at pre-study and post-study, and endpoint responses to treatment will be summarized and graphed as described above. Wilcoxon rank-sum tests will be used to compare endpoint responses to treatment for differences between the metformin and no-metformin treatment arms.

Analysis plan for secondary endpoints measured in tissue: The secondary endpoints measured in tissue will be the expression levels of mRNAs and miRs. Endpoints measured in tumor tissue, adjacent NTU tissue, and tumor-NTU differences will be summarized and graphed as described above. Wilcoxon rank-sum tests will be used to compare endpoints measured in tumor, and likewise endpoints measured in adjacent NTU tissue, for differences between the metformin and no-metformin treatment arms.

Sample Size and Power: There will be 20 subjects on each treatment arm, yielding a total of 40 subjects. The two-sided Wilcoxon rank-sum test will be used at 10% alpha to compare all endpoints and endpoint responses for differences between the metformin arm and the no-metformin arm. This study will be considered sufficiently powered to meet research objectives if the Wilcoxon rank-sum test has >90% power at 10% alpha to detect a treatment-arm difference of 1.0 SDs or more. Statistical power of the Wilcoxon rank-sum test was calculated using the 2-sample t-test module of PASS 2011 by selecting options corresponding to the worst-case scenario of underlying normal distributions with unknown SDs. Under this worst case scenario, 20 subjects per treatment arm (for a total of 40 subjects) give the two-sided Wilcoxon rank-sum test 91.6% power at 10% alpha to detect a difference of 1.0 SDs between the metformin and no-metformin arms, thereby establishing that this study is sufficiently powered to meet research objectives.

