Official Title: A Randomized Pilot Study to Evaluate the Effects of a Short Course of Metformin versus No Therapy in the Period Prior to Hysterectomy for Grade 1-2 Adenocarcinoma of the Endometrium in Obese Non-Diabetic Women

Protocol - Statistical Analysis Plan, v10 dated 5/24/2016

Data Handling and Recordkeeping

The PI will carefully monitor study procedures to protect the safety of research subjects, the quality of the data and the integrity of the study. The data will be kept in an electronic database in the office of clinical trials at the Winthrop P. Rockefeller Cancer Institute. Only the PI and Co-I, CRAs, regulatory personnel, biostatistician and lab personnel performing the analyses will have access to the data. In the event that a subject fails screening, only the eligibility criteria case report form will be completed.

Monitoring

Medical Monitor: The Medical Monitor, Principal Investigator and study staff will meet quarterly, once the PI has monitored the data, to review safety data (adverse events, serious adverse events and other scientific observations).

Study Monitor: The study will be monitored to ensure that the rights and well-being of human subjects are protected, that the data are accurate, complete and verifiable from source documents and that the trial is conducted in compliance with currently approved protocol/amendments on a quarterly basis.

Statistical Considerations

General approach: For each tissue endpoint, the tumor-NTU difference will be calculated in each patient as the paired difference in values between tumor and adjacent NTU tissue. For each blood endpoint, the endpoint response to treatment will be calculated in each patient as the paired difference between post-study and pre-study values. All data will be summarized by treatment arm as the mean, standard deviation (SD), median, and range, and will be graphed as box plots. Tumor-NTU differences and endpoint responses will be compared against zero via signed-rank test within each treatment arm. Treatment arms will be compared to each other for differences via Wilcoxon rank-sum tests, with additional details provided below. All statistical comparisons will be two-sided, and will employ a 10% alpha to reduce Type II error in this pilot proof-of-concept study.

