Sample Size and Power: There will be 20 subjects on each treatment arm, yielding a total of 40 subjects. The two-sided Wilcoxon rank-sum test will be used at 10% alpha to compare all endpoints and endpoint responses for differences between the metformin arm and the no-metformin arm. This study will be considered sufficiently powered to meet research objectives if the Wilcoxon rank-sum test has >90% power at 10% alpha to detect a treatment-arm difference of 1.0 SDs or more. Statistical power of the Wilcoxon rank-sum test was calculated using the 2-sample t-test module of PASS 2011 by selecting options corresponding to the worst-case scenario of underlying normal distributions with unknown SDs. Under this worst case scenario, 20 subjects per treatment arm (for a total of 40 subjects) give the two-sided Wilcoxon rank-sum test 91.6% power at 10% alpha to detect a difference of 1.0 SDs between the metformin and no-metformin arms, thereby establishing that this study is sufficiently powered to meet research objectives.

Dissemination of Data

The results will be analyzed after the analysis of all the blood and tissue samples. Then the two groups will be compared and the statistical analysis will be performed. The results will be submitted for presentation at national meetings, manuscripts will be written for publication and the data will be used to apply for additional funding from federal agencies including the National Institutes of Health/National Cancer Institute (NIH/NCI).

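### Randomisation is stratified by BMI but the between-arm tests ignore the strata, so if BMI is materially related to a marker the planned test is conservative and gives up power

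*Protocol*

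**What the plan says.** Protocol, Trial Design, section A, sets out "stratified block randomization with randomly chosen blocks of size 2, 4, and 6, and with BMI as the stratification factor". Two envelope sets are kept, "one set for subjects with BMI from 30 to 39.9 and one set for subject with BMI of 40 or higher". The stated purpose is to limit imbalance between the arms.

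The Statistical Considerations text is the same in the protocol and the SAP. The general approach reads: "Treatment arms will be compared to each other for differences via Wilcoxon rank-sum tests, with additional details provided below". For the primary tissue markers, "Wilcoxon rank-sum tests will be used to compare endpoints measured in tumor, and likewise endpoints measured in adjacent NTU tissue". For blood and plasma endpoints, "Wilcoxon rank-sum tests will be used to compare endpoint responses to treatment for differences between the metformin and no-metformin treatment arms". None of these sentences, nor the one on tissue mRNA and miR levels, mentions a stratified test or a BMI covariate. BMI otherwise appears in the exploratory objectives, for which no analysis method is given.

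The general approach also fixes the error rate: "All statistical comparisons will be two-sided, and will employ a 10% alpha to reduce Type II error in this pilot proof-of-concept study". The power paragraph counts the study as sufficiently powered if the rank-sum test "has >90% power at 10% alpha to detect a treatment-arm difference of 1.0 SDs or more", and reports 91.6% with 20 patients per arm. It does not say whether that SD is taken within BMI stratum or over all patients in an arm.

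**The concern.** Blocking within BMI strata makes the arms nearly equal in their BMI mix, so variation between strata largely drops out of the arm difference. The pooled rank-sum test does not know this. Its null variance is that of an unrestricted allocation of all 40 patients and still contains the between-stratum variation. If the tested value differs materially between strata, the test rejects less often than its nominal 10% under the null, and less often than it could under the alternative.

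The primary tissue markers are the most exposed, because they are compared between arms as levels at surgery; tissue mRNA and miR levels are treated the same way. Blood and plasma endpoints are tested as post-minus-pre change, so there BMI would have to predict the change.

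At stake is power, not false positives. The plan accepts a 10% alpha in order to reduce Type II error, and a conservative test hands part of that back.

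**Working it through.** **Inputs from the documents.** 40 patients, 1:1; two BMI strata; blocks of 2, 4 and 6 within stratum; two-sided 10% alpha; difference of 1.0 SD; criterion above 90% power; normal data, as in the plan's power calculation.

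**Assumptions, because the documents give neither.** The stratum split (24/16, with 28/12 and 20/20 as variants), and the shift *g* in the tested value between strata, in within-stratum SDs.

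**Step 1: the plan's own figure.** The rank-sum test's efficiency relative to the t-test for normal data is 3/π = 0.955. Then 20 × 0.955 = 19.1, or 19 per arm in whole patients. The noncentral t power with 19 per arm, 36 degrees of freedom and noncentrality √(19/2) = 3.08 is 91.6%. The stated figure reproduces.

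**Step 2: rough size of the effect.** With a share *p* in the upper stratum, the within-arm variance is 1 + p(1−p)g². If the blocking balanced the strata perfectly, the arm contrast would vary only with the within-stratum variance of 1. The true size would then be about 2Φ(−1.645 × √(1 + p(1−p)g²)). For p = 0.4:

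- g = 0.75: variance 1 + 0.24 × 0.5625 = 1.135, so strata carry 0.135/1.135 = 12% of it. Critical value 1.645 × 1.065 = 1.75; size about 8.0%.
- g = 1.0: variance 1.24, so strata carry 0.24/1.24 = 19%. Critical value 1.645 × 1.114 = 1.83; size about 6.7%.

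**Step 3: simulation.** 100,000 replicates per cell, with blocks drawn separately in each stratum, split 24/16, large-sample tests. Each cell shows the planned unstratified test, then van Elteren. The total SD is √(1 + p(1−p)g²).

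| Shift *g* | Size, % | Power, 1.0 within-stratum SD, % | Power, 1.0 total SD, % |
|---|---|---|---|
| 0 | 10.1 / 10.1 | 91.8 / 91.0 | same |
| 0.25 | – | 91.4 / 91.0 | – |
| 0.5 | 9.3 / 10.1 | 90.7 / 90.9 | – |
| 0.75 | 8.2 / 10.1 | 89.6 / 91.0 | 92.5 / 93.6 |
| 1.0 | 7.1 / 10.2 | 87.7 / 90.9 | 93.1 / 95.2 |

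The simulated sizes sit slightly above the rough values in step 2, as expected when incomplete blocks leave some imbalance.

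**Step 4: other splits, g = 1.0, within-stratum SD.** 28/12: size 7.3%, power 88.4% against 91.1%. 20/20: size 6.7%, power 87.4% against 90.9%.

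**Step 5: separate check.** A second simulation (20,000 trials per cell) drew stratum membership at random, with 50% or 30% in the upper stratum. At g = 0.75 the planned test has size 8.1% and 8.5%, and power 89.8% and 90.3%, against 91.3% and 91.4% for van Elteren. At g = 1.5 its size is 4.4% and 5.2%, and its power 81.5% and 83.4%, against 90.7% in both cases.

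**The case against.** The case for leaving the plan alone has real weight.

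- **The condition is unverified.** No figure in the documents links BMI to marker level among obese patients, and everyone enrolled already has a BMI of at least 30. The background section ties obesity to estrogen-driven proliferation and to insulin, which makes a relation plausible but gives it no size. This stands.
- **The total-SD reading may be the natural one.** The power came from a two-sample module and the paragraph never mentions strata, so its SD is plausibly the within-arm SD. On that reading the planned test exceeds both the criterion and the stated 91.6%. The loss is then only relative to a stratified test: 1.1 points at a shift of 0.75 and 2.1 at 1.0. This also stands.
- **The threshold depends on the split.** With 34/6 and a shift of 0.75, the planned test has size 9.3% and power 90.4%, against 91.0%. A small upper stratum shrinks the gain but does not reverse it.
- **The change may reach too far.** For change-from-baseline endpoints unrelated to BMI, stratifying costs 0.5 to 0.8 point. True, but that cost is small, and the tissue mRNA and miR endpoints, which are also secondary, are compared as levels like the primary markers.
- **Van Elteren is not the only candidate.** An aligned-rank test did slightly better in the second simulation (91.9% against 91.3% at a shift of 0.75, half the patients in each stratum). Either would serve if named in advance.

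These points limit the size of the concern. They do not remove the mismatch between design and analysis.

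**Conclusion.** The concern holds, conditionally. The strata used to randomise are not used in any between-arm test. At the three splits in steps 3 and 4, a BMI-stratum shift of about 0.75 within-stratum SD or more makes the planned test visibly conservative: size about 8% at 0.75 and about 7% at 1.0, against a nominal 10%. At 24/16 it gives up 1 to 3 points of power against van Elteren over that range.

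Power drops below the plan's 90% criterion only if 1.0 SD means the within-stratum SD and the shift is about 0.7 SD or more at a 24/16 split; with a smaller upper stratum the crossing comes later. Near 0.5 SD the two tests are about equal. Below about 0.4 SD the unstratified test is as good or better, by up to 0.8 point. The planned test remains valid. Everything rests on normal data and on the assumed shift and split.

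**What to change.** Add to the SAP:

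> Between-arm comparisons of the primary IHC tissue endpoints and of the continuous secondary endpoints will use the two-sided van Elteren test (rank-sum stratified by randomisation BMI stratum, 30–39.9 versus 40 or higher) at 10% alpha. The unstratified rank-sum test will be reported as a sensitivity analysis.

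Leave the adverse-event grade comparison as planned. In the power paragraph, state whether 1.0 SD is a within-stratum or a total SD.

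The change needs no new data, since the envelope set used records each patient's stratum. The price is 0.5 to 0.8 point of power for any endpoint unrelated to BMI. The choice should be fixed before results are seen: the trial is open-label, and picking between the two tests afterwards would be open to challenge.
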